1. SIGNIFICANCE

1.1. Improving caries detection is a high oral health priority

Caries is the world's most common dental disease. The WHO estimates that 60-90% of school children and nearly all adults have dental caries at some point in time(1). If carious lesions are detected early enough, i.e. before cavitation, they can be arrested and remineralized by non-surgical means. When left undetected, they could evolve into more serious and destructive conditions that may require expensive restorations, endodontic treatment, and, in some cases extractions. Despite advances made in dental imaging including digital detection and computed tomography (CT), *the diagnostic accuracy for caries has not seen significant improvement in many years and remains low.*

[figure not shown]

Figure 1: 1st row: 2D intraoral x-ray (left) and dental CBCT (right). 2nd row: schematics of caries, vertical root fracture and periodontal bone loss, which are difficult to detect with the current technologies.

The sensitivity of 2D intraoral radiography, the current gold standard for caries diagnosis, ranges from 30% to 70% for different types of caries, due to the fundamental limitation of structure superimposition (2, 3). Cone-beam CT (CBCT) requires as much as 100X the radiation, but does NOT improve caries detection due to its inferior resolution and imaging artifacts compared with intraoral imaging (4-8). The diagnostic accuracy for some other common dental conditions such as root fractures, and periodontal bone loss (**Figure 1**) have also remained low (9, 10). There is a clear *clinical and market need for better diagnostic technologies.*

1.2. We have invented a new technology with significantly increased sensitivity

Our invention, stationary intraoral tomosynthesis (s-IOT), overcomes the limitations of the current dental imaging technologies for diagnosis of dentoalveolar diseases(11, 12). It provides depth information and removes structural overlaps that obscure anatomical details in 2D imaging. It offers better in-plane resolution, less

imaging artifact, and faster image acquisition at lower dose and cost comparing to CBCT (Figure 2). Our preliminary results have shown that s-IOT provides significantly increased detection sensitivity, more accurate assessment of lesion depth and improved interpretation ease across a wide variety of clinical settings compared to the current dental imaging technologies.

	
Key features:
 
 • Significantly higher sensitivity than 2D x-ray and CT • Low dose (same as 2D intraoral) • Low cost compared to CT • Short image time (1 s) • Seamless integration with current data management system • Perform all tasks of current 2D intraoral

Figure 2: An illustration of the s-IOT device and its key advantages comparing to 2D intraoral and CBCT.
	

The clinical applications of s-IOT are not limited to caries detection, but include secondary caries detection, root fracture detection, alveolar bone assessment, root anatomy and periapical assessment, 3D assessment of dental developmental anomalies, and preliminary implant site assessment. Early disease detection and treatment will promote the oral health of patients worldwide.

1.3. **Pathway for clinical translation and commercialization**

The dental community has received the s-IOT technology enthusiastically. Over 80% of the 250 NC dentists surveyed expressed interests in purchasing this device at our estimated price range. The research won an award from the dental association, and was recently featured in “*Dentistry Today*” and on the WRAL Evening News (<http://wral.com/14923174>).

Steps toward translation and commercialization: (1) The feasibility study was performed with funding from a recently completed NIH SBIR grant; (2) Two patent applications were filed by UNC and licensed by Xintek; (3) Xintek formed a new subsidiary XinVivo to commercialize the technology; (4) Seed equity investment has been secured to construct the first clinical prototype; and (5) Potential partnerships with market leaders (Carestream Dental and Planmeca) are under discussion.

This NC TraCS grant is critical to fund the first patient evaluation at the UNC Oral and Maxillofacial Radiology Clinic, and to further advance the technology.

[figure not shown]
2. INNOVATION

2.1. s-IOT enabled by the CNT x-ray source array technology

Digital tomosynthesis uses a series of limited-angle projection images to produce a 3D representation of the object (13). A variation of this technique called Tuned Aperture CT(14) (TACT) was shown to improve the diagnostic accuracy for a number of tasks compared to 2D intraoral x-ray in bench-top phantom studies (14, 15). The technology however was not feasible for patient imaging. It took ~30 minutes for a scan (vs. ~ 1 s for a 2D x-ray) and required high operator skills for positioning, because the x-ray tube needed to be precisely moved and positioned at different locations to acquire the multiple projection images. The image reconstruction time was also very long due to inefficient algorithm.

The working mechanism of s-IOT is illustrated in **Figure 3**: (1) A carbon nanotube (CNT) x-ray array technology invented by our team at UNC(16-18) is utilized to *generate a scanning x-ray from different directions without any mechanical motion*; (2) A high-frame-rate digital intraoral sensor captures the projection images in synchronization with the x-ray exposure; (3)

An optical pattern recognition method developed in our lab is used to determine the imaging geometry; and (4) A high-speed iterative reconstruction algorithm written by us (19) processes the projection images to generate tomosynthesis image slices in real-time. *In s-IOT, a complete 3D scan takes less than 1 second; the total imaging dose used is the same as a single 2D intraoral radiograph.* The 3D tomosynthesis slices are reconstructed and displayed layer by layer in the depth direction to “virtually dissect” the object.

2.2. Preliminary results: s-IOT outperforms current dental imaging modalities.

A bench-top s-IOT device was constructed and used for evaluation and system optimization. The performance was compared with clinical 2D intraoral x-ray by imaging phantoms (20) and extracted human teeth. **Figure 3** shows examples of phantom images where: (1) **carious lesions are missed or barely discernable on the 2D image (B), but are clearly visible in the tomosynthesis reconstruction slices (C,D)**; (2) s-IOT clearly resolved the front and back **roots** of the upper molar teeth (C, D) that was overlapped in the 2D image (B); and (3) s-IOT identified **root fractures (D)** that was missing in 2D (B).

Certification: The system will be installed in the UNC-School of Dentistry (SOD) Radiology Clinic. Product safety testing and certification will be performed by MET Laboratories (www.metlabs.com), which we have previously engaged for two other x-ray imaging systems (27). We will work with the UNC EHS to ensure the system satisfies radiation safety requirement. SOD has committed the space for this study.

3.2. SPECIFIC AIM 2: Clinical Evaluation and Patient Experience

Patient selection and image acquisition: Fifty patients referred to the UNC Section of Oral and Maxillofacial Radiology for bitewing or full-mouth series exams will be recruited following completion of their ordered radiographic exams. Patients with moderate caries will be approached about participation in the study. Consenting patients will then receive a 4-bitewing exam using the s-IOT system. We will acquire both the ordered conventional radiographic exam and the s-IOT exam. The same group of patients will be tested for both caries detection evaluation and patient care experience.

Caries detection: Three UNC SOD dentists will be recruited to independently review each radiographic exam to diagnose caries presence/absence. Discrepancies between reviewers will be reconciled by consensus.

Verification: In vivo assessment of the true state of a proximal tooth surface is challenging. For the purpose of this study, cases where a proximal tooth surface received a caries diagnosis on the s-IOT images and not on the conventional images, or vice versa, are of particular interest. For these cases, the patient's clinician will be contacted to perform reversible mild clinical tooth separation to allow visual assessment of caries status.

Data analysis: The goal of the data analysis is to test (1) whether differences in the caries detection rate between s-IOT and conventional radiographs are present and (2), if so, whether these differences result from s-IOT being more sensitive. With 50 patients x 4 images/patient x ~4 teeth/image x 2 surfaces/tooth = 1600 surfaces, we expect sufficient statistical power to detect diagnostic differences.

A statistical test for paired nominal data, such as the McNemar's test, would be used to test the first hypothesis while accounting for within-patient and within-tooth/image correlations. Sensitivity, specificity and diagnostic accuracy are calculated from the clinically verified cases to characterize and quantify the modalities and will be compared regarding the second component of the hypothesis. To obtain proper inference to account for complex correlations within the same patient, or the same tooth, or the same image, resampling approach based on bootstrapping over 50 patients will be used to obtain correct variances for all statistics. NC TraCS statistician ([name]) will help perform the above data analysis.

Patient experience: Each subject will be given a brief survey regarding the overall comfort, time, and experience differences between the two imaging systems. The investigators will also complete a similar brief survey regarding the overall confidence in diagnosis, time, and the number of required radiographic re-takes. The statistical difference between two imaging systems will be analyzed.

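### Re-takes, time and comfort are compared between a fixed 4-bitewing s-IOT exam and an ordered conventional exam of varying extent, with no adjustment for the number or type of views

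*Combined protocol and SAP*

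**What the plan says.** All of the relevant text is in section 3.2 (Specific Aim 2), with one related sentence in section 4.

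- **Who is recruited.** "Fifty patients referred to the UNC Section of Oral and Maxillofacial Radiology for bitewing or full-mouth series exams will be recruited". They are "recruited following completion of their ordered radiographic exams", so the conventional exam is finished before the study begins for that patient.
- **s-IOT exam.** This is fixed: "Consenting patients will then receive a 4-bitewing exam using the s-IOT system".
- **Conventional exam.** This is not fixed: "We will acquire both the ordered conventional radiographic exam and the s-IOT exam". The number of images in an ordered bitewing exam or in a full-mouth series is not given, nor is the expected mix of the two.
- **Patient experience.** "The same group of patients will be tested for both caries detection evaluation and patient care experience". For the patient, "Each subject will be given a brief survey regarding the overall comfort, time, and experience differences between the two imaging systems". A similar investigator survey covers diagnostic confidence, time and how many re-takes were needed. The analysis is described only as a statistical comparison of the two systems, with no denominator, matching, stratification or restriction.
- **Caries detection.** Three dentists "independently review each radiographic exam to diagnose caries presence/absence". The size calculation reads "With 50 patients x 4 images/patient x ~4 teeth/image x 2 surfaces/tooth = 1600 surfaces". Verification concerns proximal surfaces called carious on one modality and not on the other.
- **Section 4** likens the s-IOT dose to that of a conventional 2D bitewing exam.

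**The concern.** One side of the comparison is always four bitewings. The other side varies with the referral. A count of re-takes rises with the number of exposures, whichever device makes them. A patient's sense of how long an exam took, or how uncomfortable it was, may also depend on how many sensor placements it involved and where. If the two exams differ in extent, a difference reported between systems may come partly from the referral and not from the device, and a larger sample would not remove it.

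Patient experience is named in the title of Aim 2, and the same 50 patients supply both it and the detection data. A statement that the new device needs fewer re-takes, or is quicker or more comfortable, would rest on this comparison.

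**Working it through.** **The plan's own figure.** 50 patients × 4 images × 4 teeth × 2 surfaces = 1600 surfaces, which reproduces. That is 4 × 4 × 2 = 32 surfaces per patient. It is a count of surfaces for detection and says nothing about how re-takes, time or comfort are to be compared.

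**Inputs for the re-take illustration.** From the documents: 50 patients and 4 s-IOT images each, so 50 × 4 = 200 s-IOT images. Assumed, because the documents do not give them:

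- f, the share of patients with a full-mouth series: 0, 10% or 25%
- K, images per full-mouth series: 10 to 20
- B, images per ordered bitewing exam: 4 or 2
- an equal re-take rate per image for both systems and all views, so that there is no device difference

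**Formula.** Expected re-takes equal images times the per-image rate. At equal rates, the conventional to s-IOT ratio of raw counts is

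ratio = [f × K + (1 − f) × B] / 4.

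**Worked case, f = 10%.** There are 5 full-mouth and 45 bitewing patients.

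- B = 4: K = 10 gives (5 × 10 + 45 × 4)/200 = 230/200 = 1.15; K = 20 gives (100 + 180)/200 = 1.40.
- B = 2: K = 10 gives (50 + 90)/200 = 0.70; K = 20 gives (100 + 90)/200 = 0.95.

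| Full-mouth share | B = 4, K = 10 to 20 | B = 2, K = 10 to 20 |
|---|---|---|
| 0 | 1.0 | 0.5 |
| 10% | 1.15 to 1.40 | 0.70 to 0.95 |
| 25% | 1.375 to 2.0 | 1.0 to 1.625 |

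With no device difference at all, the ratio can fall on either side of 1.

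**Does restricting to bitewing views suffice?** Not for raw counts. If the conventional bitewing part has 2 images, the ratio is still 2/4 = 0.5. Dividing by the number of bitewing images on each side brings it to 1 under equal rates, whatever f, K and B are.

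**Does a per-image rate over the whole series suffice?** Only if all views are re-taken equally often. Assume 4 bitewings in each full-mouth series, and let r be the re-take rate of other views relative to bitewings. The whole-series rate relative to the bitewing rate is [4 + r × (K − 4)]/K.

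- r = 0.5: 7/10 = 0.70 at K = 10, and 12/20 = 0.60 at K = 20.
- r = 2: 16/10 = 1.6 at K = 10, and 36/20 = 1.8 at K = 20.

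So re-takes per bitewing image is the sounder basis. No comparable multiple can be given for time or comfort.

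**The case against.** The best reply is that the plan already points to a bitewing-to-bitewing comparison. The surface count uses 4 images per patient, the test is paired by surface, discordance is defined by proximal surface, and section 4 names a bitewing exam as the dose comparator. For caries detection this is largely right: together these imply a common set of surfaces. A reader might infer that extra full-mouth views bias the detection comparison. The documents do not support a direction or size for that, and using the whole ordered exam as comparator would be a defensible choice. All that remains is that the views to be read are not named.

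The reply does not carry over to the experience outcomes. A surface count and a dose statement do not govern survey items or a re-take count.

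It can also be said that the survey is worded about imaging systems, that the questionnaires are not in the documents, and that nothing says raw totals will be compared. That is fair. The items may already refer to comparable images, and the supported statement is that no adjustment is specified, not that a distorted result is certain.

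Finally, every multiple above rests on assumed inputs. That also stands: the figures show sensitivity and are not estimates of a likely effect.

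**Conclusion.** The point holds in a limited form. As written, re-takes, time and comfort are compared between exams that may differ in extent, with nothing to separate the device from the number and type of views.

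Three stronger readings are tempting and should be resisted.

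- *Raw re-take counts must favour s-IOT.* This needs ordered bitewing exams to have four images, which is stated only for s-IOT. With 2 images the ratio is 0.70 to 0.95 at a 10% full-mouth share.
- *There is no problem if nobody has a full-mouth series.* This needs the same condition. With 2-image bitewing exams the ratio is 0.5 at a zero share.
- *Limiting the analysis to bitewing referrals gives a clean comparison.* It does not, because s-IOT always follows the ordered exam and order and recall effects on comfort and time remain.

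The illustrative range for re-takes, over shares of 0 to 25%, is 1.0 to 2.0 with 4-image bitewing exams and 0.5 to about 1.6 with 2-image exams. It assumes equal per-image rates and 10 to 20 images per series. Severity is minor: these are survey outcomes, and the stated goal of the data analysis is caries detection.

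**What to change.** 1. Record, for each patient, the type of exam ordered and the number of images by view.
2. Compare re-takes per bitewing image on both systems. Because the conventional exam precedes recruitment, its re-takes must be taken from the record of that exam. If views cannot be separated, report re-takes per image and state that the view types differ.
3. Word the comfort and time items to refer to the bitewing images, or report bitewing and full-mouth referrals separately.
4. State that s-IOT always comes second, so that order effects are acknowledged as a limitation.
5. As a clarification only, state that readers use the conventional bitewing views and that the analysis covers surfaces imaged on both modalities.

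**Cost.** A small re-take log, some preparation of the reading set, and survey wording that must be settled before the first patient answers. The bitewing wording keeps all 50 patients, provided they can rate that part separately. Reporting by referral type widens intervals. If an item were a yes/no preference near 50% (an assumption, as no scale is given), the 95% half-width 1.96 × √(0.25/n) is 13.9 points at n = 50. Among bitewing referrals it is 14.6 at n = 45 (10% full-mouth) and 15.9 at n = 38 (about 25%); the full-mouth group would be much less precise. Under item 5, a patient with no matching conventional bitewing views would drop 32 surfaces from the 1600, and the number dropped should be reported.

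### Does approaching patients with moderate caries after their conventional exam, which is also the comparator, bias the comparison with s-IOT?

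*Combined protocol and SAP*

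**What the plan says.** Section 3.2 (Patient selection and image acquisition) takes fifty patients sent to the oral radiology section for bitewing or full-mouth imaging. They "will be recruited following completion of their ordered radiographic exams. Patients with moderate caries will be approached about participation in the study". It then states: "We will acquire both the ordered conventional radiographic exam and the s-IOT exam". No second conventional exam is described, so the exam completed before the approach supplies the comparator images. s-IOT is performed only after consent.

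Under Caries detection, "Three UNC SOD dentists will be recruited to independently review each radiographic exam to diagnose caries presence/absence", and disagreements go to consensus. Under Data analysis, the first hypothesis is "whether differences in the caries detection rate between s-IOT and conventional radiographs are present". The second, taken up only if the first shows a difference, is whether greater s-IOT sensitivity explains it. "Sensitivity, specificity and diagnostic accuracy are calculated from the clinically verified cases", and clinical verification is sought where the two modalities disagree.

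No section defines moderate caries, gives the source of that finding or names who makes it. No section says that the conventional images are used to make it.

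**The concern.** Selecting patients on the result of one of two tests being compared is a known source of bias. If entry needs a minimum number of conventional calls, the enrolled patients are partly those in whom the conventional exam happened to score well, through true hits and through false positives. s-IOT comes after selection and gets no matching lift. Pairing within patient does not remove the asymmetry. The planned "resampling approach based on bootstrapping over 50 patients will be used to obtain correct variances for all statistics" deals with variance, not with who was enrolled. An upper limit on calls pulls the other way and can enlarge the apparent sensitivity gain.

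The setting makes this reading natural. Patients are found in an imaging clinic after the films exist, section 1.1 treats intraoral radiography as the reference for caries diagnosis, and section 3.2 concedes that "In vivo assessment of the true state of a proximal tooth surface is challenging". At stake is mainly the first hypothesis, since the second is reached only through it.

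**Working it through.** **Plan's own figure.** 50 × 4 × 4 × 2 = 1600 surfaces, which reproduces; 1600 / 50 = 32 per patient. The plan states no power inputs, so its power claim cannot be recomputed.

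**Inputs to an illustration.**
- Conventional sensitivity 0.50, the midpoint of the range in section 1.1 ("The sensitivity of 2D intraoral radiography, the current gold standard for caries diagnosis, ranges from 30% to 70"%).
- s-IOT sensitivity 0.50 × 1.36 = 0.68, reading the 36% in section 2.2 as a relative gain.
- Specificity equal for both modalities, because section 2.2 reports no loss. The value 0.95 is assumed.
- Carious surfaces per patient: mean 3.2 (assumed), Poisson or gamma-Poisson with shape 2. Calls are independent between modalities.
- Entry cut-off in conventional calls (assumed), and the probability r that a study call repeats the enrolment call (assumed; otherwise redrawn).
- Power: two-sided patient-level t test at 0.05 with 50 patients, standing in for the clustered McNemar test.

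**Closed-form check.** When the study read is independent of screening given true status, the difference is (carious surfaces per patient) × (0.68 − 0.50) / 32.
- No selection: 3.20 × 0.18 / 32 = 1.80 points.
- At least 2 calls: 3.46 × 0.18 / 32 = 1.95 and 3.75 × 0.18 / 32 = 2.11 points. Only case mix changes; the sensitivity gap stays at 18.

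**Simulation** (Poisson / gamma-Poisson; gap and difference in percentage points):

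| Entry rule, r | Sensitivity gap | Detection-rate difference | Power |
|---|---|---|---|
| none | 18.0 / 18.1 | +1.80 / +1.80 | 48 / 47% |
| ≥2, r = 0 | 18.0 / 18.0 | +1.95 / +2.12 | 54 / 58% |
| ≥2, r = 0.5 | 15.9 / 16.5 | +1.32 / +1.43 | 28 / 30% |
| ≥2, r = 1 | 13.9 / 14.9 | +0.72 / +0.75 | 12 / 12% |
| ≥3, r = 1 | 9.9 / 12.2 | −0.51 / −0.08 | not quoted |
| 2–4, r = 0 | 18.0 / 18.0 | +1.78 / +1.61 | 48 / 40% |
| 2–4, r = 1 | 19.2 / 20.7 | +2.03 / +1.58 | 69 / 41% |

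With a standard error of 0.93 / 0.96, the ≥2 rule shifts the difference by (1.95 − 1.32) / 0.93 = 0.7 SE when half the reads repeat. When all repeat, the shift is (1.95 − 0.72) / 0.93 = 1.3 SE to (2.12 − 0.75) / 0.96 = 1.4 SE. The 2–4 band shifts it by at most about 0.3 SE. A 3–6 band with r = 1 brings it to about zero.

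**Across the 30–70% sensitivity range, ≥2 rule.** At 0.30 against 0.41, the difference goes from +1.16 / +1.26 (r = 0) to +0.14 / +0.22 (r = 0.5) and −0.88 / −0.76 (r = 1). At 0.70 against 0.95, it goes from +2.67 / +2.89 (r = 0) to +2.01 / +1.99 (r = 1), with power still roughly 57 to 66%.

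**Second hypothesis.** The quantity closest to the plan's verified cases is the s-IOT-only share of discordant carious surfaces.
- Independent reads: 0.68 × 0.50 / (0.68 × 0.50 + 0.50 × 0.32) = 0.34 / 0.50 = 68%.
- ≥2 and r = 1: conventional sensitivity becomes 0.68 − 0.139 = 0.541, so the share is 0.68 × 0.459 / (0.68 × 0.459 + 0.541 × 0.32) = 0.312 / 0.485 = 64%.
- Standard error: about 50 × 3.46 × 0.50 = 86 discordant carious surfaces, so √(0.68 × 0.32 / 86) = 5 points.

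The move is under 1 SE even with every call repeated.

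**What image-free eligibility would cost.** Losing all enrichment leaves 3.20 carious surfaces per patient against 3.46 to 3.75. That is 1 − 3.20/3.46 = 8% to 1 − 3.20/3.75 = 15% fewer, with power 47–48% instead of 54–58% under selection with independent reads.

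**The case for a change.** The best case for a change is that the plan's sequence makes film-based screening the easy course, and that a separate reading does not guarantee independence. The images are the same, so a shadow that misled the screener can mislead the readers. In a second model (15% prevalence, entry at 4–10 calls), a separate read whose lesion visibility varies by patient still moved conventional sensitivity from 0.50 to 0.53. The first hypothesis is the gate to the second, so a real s-IOT advantage could be missed. Without a record of who was passed over, the effect could not be reconstructed later. Stating the source and the assessor would take a sentence.

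The mechanism stands, and so does the point about what cannot be recovered. The inference that the plan has this flaw does not. Patients arrive by referral with imaging already ordered, so a referral note or a clinical finding fits the wording equally well, and approach after the exam may only reflect when patients are in the clinic. The 12% power figure needs every study call to equal the enrolment call, although three dentists are to read independently. It also needs a floor with no ceiling, which enrols 77–82% of simulated patients and models a moderate group poorly. A band is not harmless in every version either, as the 3–6 case shows, so neither size nor direction can be attributed to this plan.

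**Conclusion.** No change is called for. The documents leave out how caries status is judged at screening, and they do not set a rule that selects on the comparator. Harm needs two further conditions that no section states: that the conventional images decide entry, and that the study reading depends on that decision beyond true caries status. If the second fails, accuracy is unbiased and only case mix moves.

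If both hold, the effect on the detection-rate difference at sensitivity 0.50 runs from negligible (2–4 calls) to loss or slight reversal (≥3 calls, all calls repeated). At 0.30 the ≥2 rule can also reverse it; at 0.70 most of it survives. The share relevant to the second hypothesis moves by under one standard error at sensitivity 0.50 with the ≥2 rule. All of this rests on assumed cut-offs, repeat rates, prevalence and specificity.

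Source, assessor and separation of readers from screening are operating details that a competent team would settle and report. Replacing the films with chart or clinical information is a fair trade-off at best: it gives up enrichment, and charts may themselves rest on earlier films.

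### The conventional exam always comes first and s-IOT second, so the patient-experience test cannot separate the imaging system from exam order or, for full-mouth patients, from exam length

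*Combined protocol and SAP*

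**What the plan says.** Section 3.2 (Patient selection and image acquisition) enrols "Fifty patients referred to the UNC Section of Oral and Maxillofacial Radiology for bitewing or full-mouth series exams". These patients "will be recruited following completion of their ordered radiographic exams", and "Consenting patients will then receive a 4-bitewing exam using the s-IOT system". The same paragraph adds: "The same group of patients will be tested for both caries detection evaluation and patient care experience".

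The Patient experience paragraph of the same section states: "Each subject will be given a brief survey regarding the overall comfort, time, and experience differences between the two imaging systems". Investigators complete a similar survey on diagnostic confidence, time and the number of re-takes. The analysis is one sentence: "The statistical difference between two imaging systems will be analyzed".

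No part of the document randomises or balances the order of the two exams, adjusts for order, or names it as a limitation. Nor does it say how a full-mouth series is to be compared with four s-IOT bitewings.

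**The concern.** Within each patient this is a two-period comparison run in a single sequence. Anything that differs between a first and a second intraoral session in the same mouth shifts every patient the same way and is counted as a system effect. Soreness or fatigue would count against s-IOT. Familiarity with the sensor, or positioning already worked out for that mouth, would count in its favour. The net direction is unknown.

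The content of the exams adds a second confounder. A full-mouth series is a longer procedure than four bitewings, so a patient who had one may report that s-IOT was quicker and more comfortable simply because fewer images were taken.

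At stake is whether the trial can say anything about s-IOT itself on comfort, time, experience or re-takes. Either a significant difference or its absence could reflect order or exam length. The planned bootstrap over patients corrects variances; it does not remove a shift common to all patients.

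**Working it through.** **The plan's own figure.** The only sizing figure is in Section 3.2 (Data analysis): "With 50 patients x 4 images/patient x ~4 teeth/image x 2 surfaces/tooth = 1600 surfaces". It reproduces: 50 × 4 × 4 × 2 = 1600. It sizes the caries comparison and has no bearing on the survey, for which the plan gives no alpha, power, effect size or scale.

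**Inputs from Section 3.2.** 50 patients; one sequence, conventional then s-IOT; ordered exam either bitewings or a full-mouth series; s-IOT always four bitewings.

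**Step 1: system against position.** Code each patient's two exams as (intercept, system, position), with system = 1 for s-IOT and position = 1 for the second exam.

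- As planned: rows (1,0,0) and (1,1,1) for all 50 patients. The system and position columns are identical: correlation 1.0, rank 2 of 3.
- For comparison, an assumed 25/25 split adds rows (1,1,0) and (1,0,1) for half the patients: correlation 0, rank 3 of 3.

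Under the planned order only the sum of the two effects can be estimated.

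**Step 2: adding exam length.** Let s be the system effect (s-IOT minus conventional), p the effect of being second, and l the effect on the conventional score of having a full-mouth series instead of bitewings. Let f be the fraction of patients with a full-mouth series. The plan does not give f, so it may lie anywhere from 0 to 1. The expected paired difference is:

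- bitewing patients: s + p
- full-mouth patients: s + p − l
- all patients pooled: s + p − f·l

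Restricting to bitewing patients, or reporting the two groups separately, takes l out of the bitewing estimate. Nothing in the data separates s from p.

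**Step 3: a hypothetical illustration.** Assume no true system difference (and no length effect), a two-sided 5% paired test, n = 50, and an order effect d in SDs of the paired difference. Then P(reject) = Φ(d√50 − 1.96) + Φ(−d√50 − 1.96).

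| Assumed d | d√50 | P(reject) |
|---|---|---|
| 0.1 | 0.71 | 0.11 |
| 0.2 | 1.41 | 0.29 |
| 0.3 | 2.12 | 0.56 |
| 0.4 | 2.83 | 0.81 |
| 0.5 | 3.54 | 0.94 |

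If d is instead expressed in SDs of a single rating, the standard error is √(2(1 − ρ)/50). At ρ = 0.5 this is 0.141 and the table is unchanged. For d = 0.3:

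- ρ = 0.3: SE = √(1.4/50) = 0.167, 0.3/0.167 = 1.79, P = 0.43
- ρ = 0.7: SE = √(0.6/50) = 0.110, 0.3/0.110 = 2.74, P = 0.78

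Every d and ρ here is an assumption. If the survey asks for one direct comparative rating, ρ does not apply at all. Steps 1 and 2 need none of these values.

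**The case against.** **The component is secondary.** The stated goals of the data analysis are both about caries detection, and Section 4 claims power only for diagnostic differences. Patient experience takes one short paragraph with no formal hypothesis. This stands, and it limits the weight of the point. A reader might infer that the caries comparison is compromised too. The documents do not support that: caries status is read from the images by three dentists, and the order in which the patient sat for the exams has little route to those readings. The same holds for diagnostic confidence.

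**The error rates are not the trial's.** A reader might take the table as the expected false-positive risk. It is a power curve with an assumed order effect in place of a treatment effect. Soreness and familiarity oppose each other, and the net effect could be near zero. This also stands.

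**Randomising the order is not a clean remedy.** It cancels a constant order effect only if there is no unequal carry-over. A full-mouth series followed by s-IOT need not carry over as much as the reverse, and balancing order does nothing about exam length. Patients are approached if they have moderate caries, and the plan does not say that this is known before the ordered exam. If it is not, patients assigned s-IOT first could receive research x-rays before their eligibility is established. Completing ordered care first is defensible in a first patient evaluation.

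**Selection by tolerance.** A reader might also infer that patients who found the conventional exam unpleasant will decline a second one and distort the result. Nothing in the documents shows this. Such patients would leave both sides of a within-patient comparison, so it would mainly be a question of generalisability.

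None of this answers the central point: the plan tests a system difference that its design cannot isolate.

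**Conclusion.** The point holds for the patient-experience component of Aim 2. System and exam order are completely confounded in all 50 patients. For those whose ordered exam is a full-mouth series, a number the plan does not state, system is also confounded with exam length. This rests on two consecutive statements about recruitment and exam sequence and on no numerical assumption.

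It is a failure of identifiability, not a shown bias, and neither its size nor its direction can be derived from the documents. The items affected are comfort, experience, re-takes and time as it relates to acquiring the images. If the time item on the investigator survey means time spent reading images, order matters much less there; the plan does not say which is meant. The change is worth making because it costs little and alters what the trial may conclude.

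**What to change.** In Section 3.2, Patient experience:

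1. Have each patient rate the conventional exam after consent and before the s-IOT exam starts, then rate s-IOT afterwards on the same items. This does not remove the confounding, but it keeps the conventional rating from being coloured by the second exam.
2. Log time and re-takes per image for both systems. Compare bitewings with bitewings, or report full-mouth patients separately.
3. Replace the test of a difference between systems with descriptive estimates and confidence intervals, labelled as s-IOT given second versus conventional given first. State fixed order as a limitation, and make no claim of a system difference on comfort, time, experience or re-takes.

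Cost: no extra patients, images or exposure; a two-part survey form; and the loss of any inferential claim on patient experience. Because the ordered exam is over before consent, its time and re-takes must come from routine clinic records, and the plan does not say whether these hold them.

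Randomising the order is an option only if eligibility can be established before the ordered exam. It would still require the assumption of no unequal carry-over, and the bitewing-to-bitewing comparison would still be needed.
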